Early reports from many centers across the country and other countries appear to indicate that the Synergy IOL implanted bilaterally is yielding very good results at all ranges, particularly at near.²⁻⁴ Anecdotally, some surgeons have reported excellent near vision with good but not great distance vision.

Prior to utilizing the Synergy IOL, our center along with many high-volume centers across the country, employed a mix and match strategy utilizing the TECNIS Symphony in the dominant eye and the TECNIS Multifocal in the non-dominant eye with good results and high patient satisfaction.⁵

We propose conducting a prospective evaluation of a mix and match strategy incorporating Symphony with InteliLight in the dominant eye and Synergy IOL in the non-dominant eye. The Symphony lens, an Extended Depth of Focus (EDOF) lens, known for its superior distance and intermediate vision, has been upgraded to the OptiBlue version (InteliLight). The Symphony with InteliLight has an enhanced echelette design and a violet light filter. The upgraded echelette design utilizes a high-resolution lathing process that helps reduce light scatter and halo intensity. The violet light filter is designed to mitigate halo, glare, and starbursts.

1. OBJECTIVE:

The purpose of this study is to evaluate the visual outcomes, visual disturbances, patient satisfaction and spectacle independence of the Symphony with InteliLight when implanted in

the dominant eye and a Synergy is implanted in the non-dominant eye in patients with or without astigmatism after routine cataract surgery.

2. STUDY ENDPOINTS:

1. Primary Endpoints:

Binocular defocus curve at 3 months

2. Secondary Endpoints:

- a. Monocular and binocular uncorrected and distance-corrected near at 40 cm visual acuity at 3 months.
- b. Monocular and binocular uncorrected and distance-corrected near at 33 cm visual acuity at 3 months
- c. Monocular and binocular uncorrected and distance-corrected intermediate (66 cm) visual acuity at 3 months
- d. Monocular and binocular uncorrected and best-corrected distance (4 m) visual acuity at 3 months
- e. To evaluate patient's vision satisfaction at 3 months
- f. To evaluate patient's spectacle independence at 3 months
- g. To evaluate visual symptoms using a questionnaire at 3 months
- h. To evaluate functional vision using a questionnaire at 3 months

3. STUDY DESIGN:

Prospective, multicenter (up to 2 site in US), non-randomized, bilateral eye study.

4. INCLUSION/EXCLUSION CRITERIA

4.1. Inclusion Criteria:

Subjects **MUST** fulfill the following conditions to qualify for enrollment into the trial

1. Subject is undergoing bilateral lens extraction with intraocular lens implantation of the Symphony with InteliLight in the dominant eye and a Synergy in the non-dominant eye.
2. Gender: Males and Females.
3. Age: 50 years and older.
4. Willing and able to provide written informed consent for participation in the study
5. Willing and able to comply with scheduled visits and other study procedures.
6. Scheduled to undergo standard cataract surgery with topical anesthesia in both eyes within 2 to 30 days between surgeries
7. Subjects who require an IOL power in the range of +5.00 D to +34.0 D only.
8. Subjects who require a toric IOL up to +3.75 D at the IOL plane (2.57 D corneal plane).
9. Potential postoperative visual acuity of 0.2 logMAR (20/32 Snellen) or better in both eyes.

4.2. Exclusion Criteria:

Subjects with **ANY** of the following conditions on the eligibility exam may **NOT** be enrolled into the trial.

1. Severe preoperative ocular pathology: amblyopia, rubella cataract, proliferative diabetic retinopathy, shallow anterior chamber, macular edema, retinal detachment, aniridia or iris atrophy, uveitis, history of iritis, iris neovascularization, medically uncontrolled glaucoma, microphthalmos or macrophthalmos, optic nerve atrophy, macular degeneration (with anticipated best postoperative visual acuity less than 20/30), advanced glaucomatous damage, etc.
2. Uncontrolled diabetes.
3. Use of any systemic or topical drug known to interfere with visual performance.
4. Contact lens use during the active treatment portion of the trial.
5. Any concurrent infectious/non-infectious conjunctivitis, keratitis or uveitis.
6. Clinically significant corneal dystrophy
7. History of chronic intraocular inflammation.
8. History of retinal detachment.
9. Pseudoexfoliation syndrome or any other condition that has the potential to weaken the zonules.
10. Previous intraocular surgery.
11. Previous corneal refractive surgery (i.e. LASIK, PRK, RK).
12. Previous keratoplasty
13. Severe dry eye
14. Pupil abnormalities
15. Anesthesia other than topical or peribulbar anesthesia (i.e. retrobulbar, general, etc).
16. Any clinically significant, serious or severe medical or psychiatric condition that may increase the risk associated with study participation or may interfere with the interpretation of study results.
17. Participation in (or current participation) any ophthalmic investigational drug or ophthalmic device trial within the previous 30 days prior to the start date of this trial.

The principal investigator reserves the right to declare a patient ineligible or non-evaluable based on medical evidence that indicates the patient is unsuitable for the trial.

4.3. Exclusion Criteria at time of surgery:

If any of the following exclusion criteria are applicable to the study eye, the subject should not continue in the study.

1. Other ocular surgery procedures, i.e. iStent, anterior vitrectomy
2. Significant vitreous loss
3. Significant anterior chamber hyphema
4. Uncontrollable intraocular pressure
5. Zonular or capsular rupture

6. Bag-sulcus, sulcus-sulcus or unknown placement of the haptics
7. Suturing of incision required at time of surgery
8. Intraocular lens tilt or decentration
9. Significant sedation or retrobulbar block during surgery
10. Other procedure, such as pupil stretch, expanders, iris hooks during surgery

Note: Any subject in which surgery has been aborted for either eye should immediately be discontinued from the study and an exit form completed for that subject. These subjects will be followed up as per the clinic standard of care, monitored for safety, and their data will be excluded from the study efficacy analysis (obtained from FDA Database Research Results Feb, 05, 2009). All adverse events will be appropriately documented and reported.

Additionally, participants who are considered to be a vulnerable subject population are not to be enrolled into the study without prior written authorization from both the Sponsor and the IRB to ensure that a description of additional safeguards are in place during the consenting and enrollment processes. Vulnerable populations include, but are not limited to, the following:

1. Prisoners
2. Nursing home residents /institutionalized individuals
3. Mentally disabled /cognitively impaired individuals
4. Sponsor employees and their family members
5. Site employees and their family members that are directly and indirectly involved with the study
6. Students of the university or the principal investigator participating in the study
7. Economically and/or educationally disadvantaged individuals
8. Comatose individuals / traumatized individuals
9. Adults who do not read and/or write
10. Hearing impaired individuals
11. Terminally ill individuals / individuals with life-threatening conditions

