5. STUDY PROCEDURES

5.1. Subject enrollment

Potential subjects will be identified from the patients presenting at the clinic. Additionally, a flyer will be placed in the check-in area and/or the in-house TV's of the different locations, on the practices website and social media as deem necessary. Once identified as a study candidate, the patient will be asked if he/she would like to participate. The sub-investigator(s), study coordinator or an appropriately trained staff member will answer any and all questions and will obtain informed consent. A copy of the informed consent document will be given to the subject. The principal investigator

will be available if the subject wants to discuss further details with him. Any testing that is part of the investigative site's standard preoperative cataract evaluation may be performed prior to the patient given consent, provided these tests are conducted within 90 days of surgery. The patient will understand that participation in the study, or declining to participate, will not affect his/her quality of care.

No subject will be enrolled into the study that does not meet the inclusion/exclusion criteria and does not consent to be enrolled in the study. Informed consent will be obtained prior to collecting any data for the study. The original documents will be maintained by the investigator as a permanent part of the subject's research records and a copy will be provided to the patient.

5.2. Informed consent:

Subjects will be consented either in person in the office or verbally over the phone.

- In person consent process: Patients being considered for enrollment who are consented in the office will be required to sign the ICF agreeing to participate in the study. A copy of the signed consent form will be given to the subject.
- Over the phone consent process: Site staff delegated to perform the informed consent process along with a witness will sign the ICF. Subject will be asked to sign the consent during visit 2. A copy of the signed consent form will be given to the subject.

5.3. Surgery Procedures:

Subjects will be implanted with the Symphony with IntelliLight in the dominant eye and a Synergy lens in the non-dominant eye. Patients will receive either a non-toric or toric IOL based on the amount of astigmatism. The target refraction for both eyes will be closest to plano.

5.4. Study Visit Schedule and Assessments (Table 1).

5.4.1. Visit Schedule: Subjects will be examined at the following intervals:

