5.4.2. Measurements and evaluations

1. Visit 1: Informed consent process will be conducted at this visit. Assessments include best-corrected Snellen visual acuity, intraocular pressure (IOP), slit lamp examination including dilated fundus exam, cataract density and type, and visual symptoms, patient satisfaction, spectacle independence and visual function

questionnaires. Any testing that is part of the site’s preoperative cataract surgery standard of care evaluation may be performed prior to signing the informed consent provided these tests are conducted within 90 days of the surgery and notation of the date performed is entered onto the CRF. The surgeon’s standard pre-cataract surgery treatment will be used in all patients

2. Visit 2: The surgeon may use his preferred cataract extraction technique (manual or laser). The lens will be implanted in the bag. The following information will be captured the day of surgery: phaco technique (manual or laser), lens implanted and power, target refraction, residual astigmatism and axis for Toric Calculator (if applicable), additional surgical procedures, intraoperative complications, and any device deficiencies. The surgeon’s standard post cataract surgery treatment will be used in all patients.

Visit 3: Slit lamp examination, manifest refraction, monocular and binocular uncorrected as well as distance corrected visual acuities will be evaluated at 4 m, 66 cm, 40 cm, 33 cm and best distance, and defocus curve. Additionally, dilated fundus exam (as deemed necessary by the investigator), visual symptoms, patient satisfaction, spectacle independence and visual function questionnaires, adverse events and any device deficiencies will be evaluated.

Table 1. Study Visit Schedule and Assessments

| | Visit 1 Screening | Visit 2 and 2A DOS | Visit 3 3-Month 90 ±15 days |
|--------------------------------|----------------------|-----------------------|-----------------------------------|
| Informed Consent | X | | |
| Inclusion/Exclusion | X | X | |
| Demographics/Ocular history | X | | |
| BCVA Snellen | X | | |
| Eye dominance | X | | |
| UCVA ETDRS (4m) | | | X* |
| UCIVA ETDRS (66 cm) | | | X* |
| UCNVA ETDRS (40 cm) | | | X* |
| UCNVA ETDRS (33 cm) | | | X* |
| UCNVA ETDRS (at best distance) | | | X* |
| Manifest refraction – Max Plus | | | X |
| BCVA ETDRS (4m) | | | X* |
| DCIVA ETDRS (66 cm) | | | X* |

| | | | |
|--------------------------------|---|---|-----|
| DCNVA ETDRS (40 cm) | | | X* |

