9. INVESTIGATIONAL PRODUCT

9.1. Description

The Symphony IntelliLight IOL (DXR00V or DXW150 – 375 – Toric II IOL) combines an echelette design (to create an extended depth of focus) with an achromatic technology (to correct chromatic aberrations) and a violet-light filter that diminishes the perception of visual disturbances such as halo, glare and starburst. The lens has been designed to provide high quality vision up to 26 inches so patients may still need to wear glasses for some activities mainly at near.

The Synergy IOL (DR00V or DFW150-375 – Synergy Toric II IOL) using TECNIS Simplicity Delivery System is a presbyopia correcting IOL designed to improve intermediate and

near vision, while maintaining distance visual acuity. This continuous range of focus lens provides a full range of vision and increased spectacle independence.

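### Read literally, inclusion criterion 8 makes needing a toric lens a condition of entry, which contradicts the objective and sections 5.3, 5.4.2 and 9.1; it needs conditional, per-eye wording

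*Combined protocol and SAP*

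**What the plan says.** Section 4.1 introduces its list as conditions that subjects must (in bold) "fulfill the following conditions to qualify for enrollment into the trial". Item 8 of that list is "Subjects who require a toric IOL up to +3.75 D at the IOL plane (2.57 D corneal plane". The item just above it, on lens power, is phrased in a similar way: "Subjects who require an IOL power in the range of +5.00 D to +34.0 D only".

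Four other places describe who is studied and what is implanted:

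- Section 1 (Objective) sets the population as patients "in patients with or without astigmatism after routine cataract surgery".
- Section 5.3 (Surgery Procedures) states: "Patients will receive either a non-toric or toric IOL based on the amount of astigmatism".
- Section 5.4.2, Visit 2, records "residual astigmatism and axis for Toric Calculator (if applicable".
- Section 9.1 gives each lens in two forms, one not labelled toric and one toric range: "The Symphony IntelliLight IOL (DXR00V or DXW150 – 375 – Toric II IOL" and "The Synergy IOL (DR00V or DFW150-375 – Synergy Toric II IOL".

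Section 5.1 ties enrolment to meeting the inclusion and exclusion criteria. Table 1 schedules an eligibility check at screening and again on the day of surgery. Section 10 requires each deviation to be documented with its date and reason.

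**The concern.** Item 8 helps to define the study population. If it is taken as a requirement, like the lens-power item before it, a patient with little or no astigmatism has to be turned away, although the objective names such patients and section 5.3 says which kind of lens they would receive. If sites follow the objective instead and enrol them, each such subject fails a listed criterion on paper, and section 10 then calls for a documented deviation. The protocol is wrong either way: it screens out part of its stated population, or it records correct enrolments as breaches.

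There is also a question of unit. Every subject receives two lenses, one in each eye, and astigmatism can differ between eyes. Item 8 speaks of the subject and does not say whether one eye or both must need a toric lens.

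**Working it through.** The point concerns consistency of wording. No sample size, power or error-rate figure enters it, and the plan states no figure to reproduce. The check is to apply item 8 to each kind of candidate and compare the result with the other sections.

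1. *Status of the item.* The list is mandatory, and section 5.1 makes enrolment depend on it.
2. *Grammar of the item.* It contains no *if* and no *where applicable*. Section 5.4.2 shows that the protocol uses such a qualifier elsewhere for toric data.
3. *Whether the limit could include zero.* An upper limit might be read as starting at no toric power at all. Section 9.1 does not support that with any clarity, because it lists the toric range (codes 150 to 375) as an alternative to a separate model for each lens.
4. *Applying the item.*

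| Candidate | Item 8 read literally | Item 8 read as a conditional limit per eye | Objective and 5.3 |
|---|---|---|---|
| Toric lens needed in both eyes, within the limit | Meets it | Meets it | Provided for |
| Toric lens needed in one eye only, within the limit | Cannot be decided | Meets it | Within the objective; one-eye case not addressed |
| Non-toric lenses in both eyes | Fails it | Meets it | Provided for |
| Toric power above the limit needed in an eye | Fails it if that eye counts | Fails it | Limit set only by item 8 |

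The readings clearly part in the second and third rows. In the third, the literal result contradicts the objective, section 5.3, the qualifier in section 5.4.2 and the model listing in section 9.1. In the second, no section settles the matter. Items 6 and 9 of the same list do say that they concern both eyes; item 8 does not.

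5. *Search for a rescuing statement.* No section says that item 8 applies only when a toric lens is needed. Table 1 does not settle it: toric lens position is marked without qualification on the day of surgery and as the investigator deems necessary at Visit 3.

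**The case against.** The best defence is that nobody would misread the item. The objective, section 5.3, the qualifier in section 5.4.2 and the model list all point one way, and nothing outside item 8 suggests a trial confined to toric lenses. The list is also loosely drafted. Item 2, which names both sexes, describes scope and is not a condition in the ordinary sense. Item 7 ends with the word *only* and item 8 does not, so item 8 can be taken as saying how far toric correction may go. The analysis in section 6.2 plans no toric versus non-toric comparison, and no endpoint is specific to subjects without astigmatism.

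Much of this stands. The intended reading is fairly clear, and that limits the severity. It does not remove the defect. Eligibility is checked item by item, at two visits under Table 1, and a checklist copied from section 4.1 would show item 8 as not met for every non-toric subject. Nor does inferred intent settle the case of a toric lens in one eye only.

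A reader might also be tempted to put numbers on the problem, either a share of candidates excluded or a corneal cut-off. The documents support neither. They give no proportion of candidates who need a toric lens. A cut-off could be built by taking model code 150 as 1.50 D and scaling by 2.57/3.75 = 0.685, which gives 1.50 × 0.685 = 1.03 D at the cornea. But the protocol does not define the code, gives the conversion only at the upper limit, and states no threshold for choosing a toric lens beyond the amount of astigmatism.

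**Conclusion.** The inconsistency is real. As worded, item 8 excludes subjects whom the objective and sections 5.3, 5.4.2 and 9.1 provide for, and it leaves the one-eye case undefined. It is an internal inconsistency of minor to moderate severity: an eligibility rule gives the wrong population if followed to the letter, but the rest of the protocol shows what was meant and the correction is simple.

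The conclusion rests on the text alone and needs no outside figure. The number of subjects affected cannot be stated from the documents. The planned enrolment of 40 in section 6.1 is unaffected.

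Two stronger conclusions that a reader might draw do not follow. One is that the trial was meant to be toric-only; the four sections cited indicate otherwise. The other is that sites would apply the item differently and so enrol different case mixes. Section 3 allows up to two sites, so there may be only one, any site also has section 5.3 to hand, and no by-site comparison is planned.

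**What to change.** Reconcile item 8 with the objective and section 5.3 by making it conditional and per eye, leaving the protocol's own limit as it stands. For example: *If a toric IOL is required in either eye, the cylinder required in that eye is no more than the limit already stated (3.75 D at the IOL plane, 2.57 D at the corneal plane). Subjects who require a non-toric IOL in one or both eyes are eligible.* Carry the same wording into the eligibility checklist used at screening and on the day of surgery. If enrolment has started, state in the amendment how non-toric subjects already enrolled are to be classified, so that they are not left on file as unexplained deviations.

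The cost is one sentence of protocol text and a matching line on the checklist. It adds no procedure, visit or subject.

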1. Visit 1: Screening and enrollment: Preoperative evaluation completed not more than eight weeks before surgery
2. Visit 2: Day of Surgery for each eye
3. Visit 3: Month 3: 90 ±15 days postoperative after second eye surgery

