5.5. Study endpoint criteria

5.5.1. Patient Completion of Study: If a study patient has completed the final visit (Visit 3) of the study, he/she is considered to have completed the study.

5.5.2. Patient Discontinuation: Each study patient may voluntarily discontinue the study at any time they choose. Study patients who cannot complete the study for administrative reasons (e.g., non-compliance, failure to meet visit schedule, etc.) will be discontinued from the study. Study patients discontinued during the enrollment phase (prior to surgery) of the study will be replaced. Subjects who are discontinued after first eye surgery before second eye surgery will also be replaced.

5.5.3. Patient Termination: A study patient will be terminated if the study patient develops any severe adverse event that may be related to the study. A study patient will receive appropriate treatment at the discretion of the investigator. Notification of termination will be clearly documented. These study patients are considered to have completed the study and will not be replaced.

5.5.4. Study Termination: The investigator with appropriate notification may terminate the study. If, after clinical observations, the investigator feels that it may be unwise to continue the study, he may stop the study.

5.5.5. Study Completion: The study will be complete when all enrolled patients have completed Visit 3 or have been terminated from the study.

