6.3. Safety Analyses

The type, severity, duration and frequency of reported ocular adverse events will be tabulated for each group. Adverse events will also be summarized for events that were considered treatment-related. Comparison of treatment groups with respect to the proportion of study patients reporting adverse events will be made using Fisher's Exact Test.

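### Subjects who exit under section 4.3, some possibly with a study lens in place, have no scheduled postoperative safety assessment and no stated place in the safety denominator

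*Combined protocol and SAP*

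**What the plan says.** **Exit rule.** Section 4.3 gives ten criteria to be judged at surgery and states: "If any of the following exclusion criteria are applicable to the study eye, the subject should not continue in the study". The list is mixed. Some entries are complications with a severity qualifier, such as "Significant vitreous loss". Others concern anesthesia or added procedures, such as "Significant sedation or retrobulbar block during surgery". Item 6 (position of the haptics) and item 8 (lens tilt or decentration) describe a lens that is in the eye.

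**Note under 4.3.** The Note opens with a narrower group: "Any subject in which surgery has been aborted for either eye should immediately be discontinued from the study". It sends those subjects to the clinic's standard-of-care follow-up and says they are "monitored for safety, and their data will be excluded from the study efficacy analysis". Its closing sentence says that all adverse events are documented and reported.

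**Collection points.** Section 5.4.2 has intraoperative complications and device deficiencies captured on the day of surgery. Table 1 schedules adverse events and device deficiencies at Visit 2/2A and at Visit 3, and at no other time. Section 5.4.1 dates the last visit from the second eye: "Visit 3: Month 3: 90 ±15 days postoperative after second eye surgery".

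**Replacement and analysis.** Section 5.5.2 adds: "Subjects who are discontinued after first eye surgery before second eye surgery will also be replaced". Section 6.3 tabulates reported ocular adverse events and plans a comparison of "the proportion of study patients reporting adverse events". It does not say which patients those are.

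**The concern.** The exit rule is triggered by operative events, and it takes the subject out before the only postoperative study visit. Loss from the 3-month safety data is therefore tied to what happened in surgery, and may be related to the outcome being summarised. Some of the subjects lost may go home with a study lens implanted, so their later course belongs to the device experience that the study is collecting.

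Two further rules compound this. Replacing first-eye exits restores the enrolled number without saying whether the replaced subject still counts for safety. And because section 6.3 gives no analysis set, the third-party consultant named in section 6.2 would have to choose the denominator. In a study of 40 subjects, one or two people in or out of that denominator visibly change an adverse event proportion.

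**Working it through.** The plan states no figure for this point, so there is nothing of its own to reproduce. The sample size of 40 rests on a rule of thumb and carries no allowance for exits. The check has two parts.

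**1. Following an exited subject through the text**

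| Situation | Day-of-surgery record | Follow-up named in the Note? | Visit 3 | Replaced? |
|---|---|---|---|---|
| Surgery aborted, first eye | Yes | Yes, standard of care | No date, because there is no second-eye surgery | Yes (5.5.2) |
| Lens implanted, 4.3 criterion met, first eye | Yes | Not expressly | No date | Yes (5.5.2) |
| Surgery aborted, second eye | Yes | Yes, standard of care | Date may be computable, but subject has left | Not stated |
| Lens implanted, 4.3 criterion met, second eye | Yes | Not expressly | Date computable, but subject has left | Not stated |

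In no row does the subject attend a scheduled postoperative study assessment. In the two rows with an implanted lens, no sentence expressly assigns follow-up or limits the data exclusion to efficacy.

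The denominator is also open from another side. Section 5.5.3 treats a patient terminated for a severe, possibly related adverse event as having completed the study, and does not replace that patient. A first-eye event could meet both that rule and the replacement rule in 5.5.2.

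**2. How many subjects**

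Inputs:
- 40 subjects (section 6.1), two eyes each.
- Per-eye probability p of any 4.3 event: assumed, 1% to 5%. The documents give no rate.
- The two eyes of a subject are treated as independent (assumption).

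Formulas, for 40 subjects starting surgery and before any replacement:
- All exits: 40 × [1 − (1 − p)²]
- First-eye exits, with no Visit 3 date: 40 × p
- Second-eye exits: 40 × (1 − p) × p
- Chance of at least one exit: 1 − (1 − p)^80

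Results:
- p = 1%: 1 − 0.99² = 1.99%, and 40 × 0.0199 = 0.8 exits. First eye 40 × 0.01 = 0.4; second eye 40 × 0.99 × 0.01 = 0.4. Chance of at least one: 55%.
- p = 2%: 1 − 0.98² = 3.96%, and 40 × 0.0396 = 1.6 exits. First eye 0.8; second eye 0.8. Chance of at least one: 80%.
- p = 5%: 1 − 0.95² = 9.75%, and 40 × 0.0975 = 3.9 exits. First eye 2.0; second eye 40 × 0.95 × 0.05 = 1.9. Chance of at least one: 98%.

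Over the assumed range, then, at least one such subject is more likely than not.

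**The case against.** The strongest reply is that the plan already protects safety data. Intraoperative complications and adverse events are recorded at Visit 2/2A. The Note removes data from the efficacy analysis only. Its last sentence on reporting adverse events carries no express limit to aborted surgery, and section 6.3 is not restricted to completers. Safety is neither an objective nor an endpoint, and section 9.2 confines implantation to uncomplicated routine surgery, so a 3-month result in such patients fits the intended scope.

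Much of this stands, and it rules out two stronger readings that a reader might infer.

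- That every subject with an intraoperative complication is removed. The documents do not support this: the list is specific, vitreous loss and hyphema count only when significant, unlisted complications do not trigger exit, and some items are not complications at all.
- That the safety results would describe only uncomplicated surgery. This is not supported either: the operative event is captured on the day, and nothing in 6.3 drops it from the tabulation.

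Nor do the documents show that exited subjects are the ones at highest risk of later ocular events. That is plausible for some items on the list, but no passage says it.

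The reply does not reach the postoperative course. Even if the Note's last sentence covers every exit, it supplies no time point, no assessments and no denominator. The missing Visit 3 date is limited to subjects who never have second-eye surgery; second-eye exits have left the study for a different reason.

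**Conclusion.** The point holds for postoperative safety, not for the recording of operative events. Applied as written, the plan collects its 3-month safety data at a study visit only from subjects without a 4.3 event. For those who exit, later adverse events depend on unscheduled routine care, which is expressly provided only after aborted surgery, and their place in the section 6.3 proportion is undefined.

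Under the assumed rates this concerns a handful of subjects at most. The expected numbers are illustrations that rest on the assumed rate and on independence of the two eyes; they are not predictions. The textual finding depends on neither. Because a stated rule produces the selective loss, this is more than an omitted detail, and it should be corrected.

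**What to change.** Leave unchanged who exits and how they are treated. Change only data collection and analysis:

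1. Reword the Note under 4.3 so that its safety monitoring, adverse event reporting and efficacy-only data exclusion apply to all 4.3 exits, not just to aborted surgery.
2. In section 6.3, define the safety set as every subject in whom study surgery was started in at least one eye, including subjects later replaced under 5.5.2.
3. For exited subjects, record a safety close-out at 90 ±15 days after their last study surgery, drawn from standard-of-care follow-up: adverse events, device deficiencies, and slit lamp and acuity findings where available.
4. Tabulate exits by 4.3 item, by eye, and by whether a study lens was left in place.

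The cost is some protocol wording and one extra CRF page for a few subjects. The reported adverse event proportion may look slightly less favourable. Efficacy analyses are unaffected.
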